6.6.2.6 The development of a clinical and/or radiographic finding

consistent with metastatic disease (e.g., a pulmonary metastasis).

6.6.3 Disease-Specific Survival- The time to disease-specific death will be measured from the date of the adenovirus injection to the date of death due to prostate cancer. Causes of death may require review by the study PI or designee. Death due to prostate cancer will be defined as:

- 6.6.3.1** Primary cause of death certified as due to prostate cancer.
- 6.6.3.2** Death in association with any ONE of the following conditions:
 - 6.6.3.2.1** Further clinical tumor progression occurring after initiation of additional salvage therapy such as ADT.
 - 6.6.3.2.2** A rise in serum PSA that exceeds 1.0 ng/mL on at least two consecutive occasions during or after salvage ADT.
 - 6.6.3.2.3** Disease progression in the absence of any prostate cancer therapy.
 - 6.6.3.2.4** Death from a complication of prostate cancer therapy, irrespective of disease status.

6.6.4 Survival- The survival time will be measured from the date of the adenovirus injection to the date of death. All subjects will be followed for survival. Every effort should be made to document the cause of death. Post-mortem examination will be carried out when feasible and a copy of the final autopsy report should be sent to the DCC.

7.0 DATA COLLECTION

7.1 Data Collection and Management

The Data Coordinating Center (DCC) is headed by [name], and is located in the Department of Radiation Oncology, Henry Ford Health System (HFHS). [name] has over 10 years experience in managing clinical trial databases. The DCC will use a Microsoft Access database for data collection using a set of Standard Operating Procedure (SOPs) developed by [name] and the study coordinator.

7.2 Standard Operating Procedures

Standard Operating Procedures (SOPs) have been developed by [name] and the study coordinator to be compliant with FDA regulations and implemented at the DCC for FDA regulated clinical trials. SOPs were developed using the FDA Good Clinical Practice Guidelines.

7.3 Case Report Forms

Case Report Forms (CRFs) have been developed specifically for this trial. The

database will be created to match with CRFs so that the data structure provides fast, efficient, and accurate data processing.

7.4 Database and Data Management

The database for this study will be implemented using a Microsoft Access database housed on a secure departmental drive. Access is a relational database with security options that limit the ability to access the data to specified people. The database structure will be set up according to the CRFs. Specific queries can be run to check for data discrepancies and missing fields. An independent monitor will conduct audits of the data for completion and accuracy no less than one time per year.

7.5 Plan for the Site Initialization

Subjects will be enrolled at the Henry Ford Health System only. After receiving all required federal (FDA, OBA) and local (IRB, IBC) approvals, Drs. [name], [name] and [name] will conduct the site initiation. They will meet with the study nurse and clinical coordinator to discuss the following: study drug, study protocol, subject enrollment, drug accountability, CRFs and instructions for completion of CRF and CRF submission, and adverse event (AE) reporting. A follow-up meeting(s) will be conducted, if one meeting is not sufficient. During subject enrollment and follow-up, Drs. [name] and [name], and [name], will be available to answer questions regarding administrative issues, enrollment, CRF data collection and quality assurance. The key investigators will meet on a regular basis to go over issues encountered during the study.

7.6 Subject Registration

Subject registration is described in **Section 4.0**. After receiving the registration information, the DCC will generate the subject's schedule for follow-up.

7.7 CRF Data Collection and Data Management

CRF data is collected based on the sources of truth (e.g., medical records). Data sources will include subject interviews (subject history, adverse events), physical examination, histology/pathology reports, all laboratory data, and medical records. Subjects will be identified by study subject number and initials (first, middle, last); if there is no middle initial, a hyphen will be used (first-last). Last names with apostrophes will be identified by the first letter of the last name. Completed CRFs will be entered into the study database by study staff on a regular basis.

Data entry is summarized in **Table 10**.

Table 10. Summary of Data Submission	
Case Report Form	Due
Eligibility Checklist	At registration
Registration Form	Within 2 weeks of registration
Pre-Treatment Conditions	Within 2 weeks of registration
Concomitant Medications	Within 2 weeks of registration
Adenovirus Injection Summary	Within 2 weeks of adenovirus injection
Prodrug Therapy	Within 2 weeks of completion of prodrug therapy regimen
Blood Labs	Within 2 weeks of blood draw
Toxicity Assessment	Within 2 weeks of toxicity assessment
SAE That Require Reporting	-24 h by phone/FAX/email -Written report within 10 calendar days
Adenoviral DNA in Blood	Within 90 days of adenovirus injection
On-site Physician Assessment	Within 2 weeks of assessment
Discontinuation of Study Therapy	Within 2 weeks of discontinuation
Death Report	If ≤ 30 days from adenovirus injection: -24 h by phone/FAX/email -Written report within 10 calendar days If > 30 days from adenovirus injection: -Within 2 weeks of learning of event
Long-Term Follow-Up	Within 2 weeks of assessment
EPIC and EQ5D	Within 2 weeks of assessment

7.8 Quality Assurance Plan to Ensure Data Quality

Data quality assurances (QA) are applied both at the DCC and clinical sites. Features of the QA plan at the DCC include:

- 7.8.1 Initial review of forms
- 7.8.2 Check for possible missing forms
- 7.8.3 CRF data field checks for missing, miscodes and outliers
- 7.8.4 Code for tracking person who completed forms
- 7.8.5 Data consistency checks (within or across the forms)
- 7.8.6 Generation of queries and an electronic audit trail

All QA queries will be documented by the data manager with respect to:

- 7.8.7 Query generation date
- 7.8.8 Date query sent to clinical site for resolution
- 7.8.9 Identification information for the form
- 7.8.10 Old (or original) value

7.8.11 Error message(s)

7.8.12 Code of person who completed the form

7.8.13 New value (may not represent a change)

7.8.14 Reason for new value

7.8.15 ID of site staff member responsible for new value

7.8.16 Date change made to database

Report forms are produced from a query table and sent to the PI for resolution. Data are processed as they are collected to ensure the smooth and systematic flow of activities, and to avoid backlogs and uneven workloads.

7.9 Confidentiality

Throughout the data collection period, the data of individual subjects will be kept confidential by DCC staff. The clinical site only holds names or other personal identifiers for conducting the subject's follow-up. Subjects' names and other personal identifiers can not appear on any data collection form, CRFs and analysis reports. The DCC must keep these strictly confidential among staff.

8.0 STATISTICAL CONSIDERATIONS

This phase 1 trial is designed to determine the toxicity of oncolytic adenovirus-mediated cytotoxic and IL-12 gene therapy in locally recurrent prostate cancer. Endpoints are classified as primary, secondary and exploratory.

8.1 Endpoints, Hypotheses and Analyses

8.1.1 Primary Endpoint

8.1.1.1 Hypothesis- Oncolytic adenovirus-mediated cytotoxic and IL-12 gene therapy is associated with acceptable toxicity.

Adverse events will be graded according to NCI's Common Terminology Criteria for Adverse Events (CTCAE) v4.03 (68). Adverse events will be collected through day 30 (day 1 being the day of the adenovirus injection).

8.1.2 Secondary Endpoints

8.1.2.1 Hypothesis 1- Oncolytic adenovirus-mediated cytotoxic and IL-12 gene therapy has an effect on serum PSA levels.

Serum PSA will be assessed according to Table 7 and compared to the subject's baseline value.

8.1.2.2 Hypothesis 2- Oncolytic adenovirus-mediated cytotoxic and IL-12 gene therapy has an effect on PSADT.

Serum PSA will be assessed according to Table 7. PSADT will be determined by logarithm regression analysis as described previously (38). PSADT prior to the study therapy will be calculated using a minimum of three PSA values including the last PSA prior to initiation of the study therapy. Subjects who do not have at least three pre-treatment PSA values will be excluded from the analysis. PSADT after the study treatment will be calculated from the nadir and will use all PSA values prior to the implementation of additional salvage therapy such as ADT.

PSADT will be calculated assuming first-order kinetics using the following equation:

$$\ln(\text{PSA}) = \beta_0 + \beta_1 t$$

where β_0 is the point where the regression line crosses the ordinate at $t = 0$ and β_1 is the number of units that $\ln(\text{PSA})$ changes for every one-unit change in time (i.e., the slope). PSADT is defined as $\ln(2) / \beta_1$. Data are evaluated for normality the ranked data are considered if data are not normal.

8.1.2.3 Hypothesis 3- Oncolytic adenovirus-mediated cytotoxic and IL-12 gene therapy has no significant effect on quality of life.

We will use two instruments to measure QOL: EPIC and EQ-5D. QOL instruments will be collected on all subjects at baseline, 6, 12 and 24 months after the adenovirus injection.

EPIC questionnaires will be completed by the subject. The questionnaires will be summarized into three endpoints of function and bother in urinary, bowel and sexual domains with a score of 0 to 100. EQ-5D will have a self-report score of 1 to 3 in five domains (mobility, self-care, usual activity, pain/discomfort and anxiety/depression), and an overall health score 10 to 100. If a subject death is related to prostate cancer or the study treatment, the worst score will be given and the subject will be included in the analysis.

Data will be evaluated for normality, data transformation or nonparametric approach will be considered if data are not normal.

For each QOL domain variable, analysis of variance and covariance (ANCOVA) will be used. Analysis will include the baseline covariates of pre-treatment domain score, covariate of time (of assessment post-treatment) and the independent

treatment variable. The analysis will start testing for treatment by time interaction, followed by testing the treatment effect at each time point if the interaction is detected at critical value 0.10, or testing the overall treatment effect or time effect at critical value of 0.05 if otherwise.

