3.3 Criteria for Subject Exclusion

Subjects with the following conditions will be excluded from the study:

- 3.3.1** PSA ≥ 100 ng/mL.
- 3.3.2** Prostate volume > 100 cc.

- 3.3.3** Pathologically positive lymph nodes or nodes > 1.0 cm on imaging. Note: nodes > 1.0 cm but biopsy negative are allowed.
- 3.3.4** Evidence of M1 metastatic disease.
- 3.3.5** Prior invasive malignancy except for non-melanoma skin cancer within 5 years of enrollment. Subjects must be disease-free for > 5 years.
- 3.3.6** Prior radical prostatectomy, cryosurgery for prostate cancer, or bilateral orchiectomy for any reason.
- 3.3.7** If the subject had prior androgen deprivation therapy (ADT), the subject exhibited biochemical failure while on ADT.
- 3.3.8** Prior systemic chemotherapy for the study cancer. Note that prior chemotherapy for a different cancer is allowed; however, subjects must be > 2 years post-completion of chemotherapy at time of registration. Subjects on Proscar therapy must stop to be eligible.
- 3.3.9** Major surgery planned within 3 months of registration.
- 3.3.10** Severe, active co-morbidity defined as:
 - 3.3.10.1** New York Heart Association Class II or greater congestive heart failure or active ventricular arrhythmia requiring medication.
 - 3.3.10.2** Chronic obstructive pulmonary disease (COPD) exacerbation or other respiratory illness requiring hospitalization within last 3 months or precluding study therapy at the time of registration.
 - 3.3.10.3** Acute infection. Acute infection is defined by any viral, bacterial, or fungal infection that requires specific therapy within 72 hours of initiation of the study therapy.
- 3.3.11** Previous history of liver disease including hepatitis.
- 3.3.12** Immunosuppressive therapy including systemic corticosteroids. Use of inhaled and topical corticosteroids is permitted.
- 3.3.13** Impaired immunity or susceptibility to serious viral infections.
- 3.3.14** Allergy to any product used in the protocol. If the subject has an allergy to Ciprofloxacin, another antibiotic can be substituted at the discretion of the treating physician.
- 3.3.15** Serious medical or psychiatric illness or concomitant medication, which, in the judgment of the principal investigator, might interfere with the subject's ability to respond to or tolerate the treatment or complete the trial.

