5.0 STUDY THERAPY AND PROTOCOL

5.1 Treatment Plan

5.1.1 Pretreatment Evaluations

5.1.1.1 History and physical examination including digital rectal exam (DRE).

5.1.1.2 Hematology- CBC/DP.

5.1.1.3 Blood chemistries- glucose, Na, K, Cl, Ca, Mg, P, CO₂, BUN, creatinine, AST/SGOT, ALT/SGPT, ALKP, bilirubin, serum protein, albumin, globulin, GFR, CPK, LDH, GGT, testosterone.

5.1.1.4 Diagnostic serum PSA.

5.1.1.5 Urinalysis, urine culture, and sensitivity.

- 5.1.1.6** Chest radiographs (PA and lateral).
- 5.1.1.7** Diagnostic imaging- bone scan and CT scan of the abdomen and pelvis within 90 days of registration.
- 5.1.1.8** Biopsy/pathology reviews- a TRUS-guided needle biopsy of the prostate (\geq 6 core) must be performed within 180 days of registration to confirm the presence of adenocarcinoma and to determine prostate volume. Biopsy cores should be kept separate, coded and submitted to Department of Pathology for analysis.
- 5.1.1.9** Molecular studies- presence of Ad5-yCD/*mutTK_{SR39}rep-hIL12* in blood by polymerase chain reaction (PCR). This is a baseline control for the post-treatment PCR assays and does not have to be completed before the subject can be enrolled.
- 5.1.1.10** Immunological studies- serum IL-12 and IFN- γ will be measured by enzyme-linked immunosorbent assay (ELISA). NK cell cytolytic activity will be measured by ^{51}Cr release or non-radioactive cytotoxicity assay. These are baseline controls for the post-treatment evaluations and do not have to be completed before the subject can be enrolled.
- 5.1.1.11** EPIC and EQ-5D instruments.
- 5.1.1.12** The subject will be required to meet with a urologic surgeon to discuss other treatments options such as salvage prostatectomy. This meeting must be documented in the patient's records.

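### Post-treatment PSADT, taken as ln(2)/slope from the nadir, has no usable value for men whose PSA is flat or still falling, and ranking does not repair this

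*Combined protocol and SAP*

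**What the plan says.** Section 2.2 lists PSADT before and after therapy as one of five secondary objectives. Section 8.1.2.2 gives the method: fit ln(PSA) on time by regression and take ln(2)/slope.

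- **After treatment:** "PSADT after the study treatment will be calculated from the nadir and will use all PSA values". Values stop counting once a man starts further salvage treatment. No minimum number or span of post-nadir values is set. Nothing is said about a nadir that is also the latest PSA, or about a zero or negative slope.
- **Before treatment:** at least three values, "including the last PSA prior to initiation of the study therapy". The only exclusion stated is this: "Subjects who do not have at least three pre-treatment PSA values will be excluded from the analysis".
- **Non-normal data:** ranks are to be considered. The plan does not say where a negative or missing PSADT would rank.
- **Drugs that affect PSA:** Section 3.3.8 states "Subjects on Proscar therapy must stop to be eligible", with no interval. Section 3.3.7 excludes a man on this condition: "If the subject had prior androgen deprivation therapy (ADT), the subject exhibited biochemical failure while on ADT". Other prior ADT is allowed, again with no interval. The cut at ADT applies only to post-treatment values.

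The section also points to the five-year report of Trial 1 for its method. Section 8.3 makes the whole analysis descriptive.

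**The concern.** PSADT is the reciprocal of a slope, and a reciprocal jumps at zero. As PSA growth slows towards nil, PSADT rises without limit; once the slope passes below zero, PSADT becomes large and negative. The best outcomes sit next to the point where the measure breaks down. Starting the fit at the nadir adds a second gap, because a man whose PSA is still falling at his last visit contributes a single point.

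The trial has 15 to 30 men and no control arm, so one man is 1/30 = 3% to 1/15 = 7% of the sample. A few missing or misplaced responders can change a before/after comparison, and the gap acts against the therapy. Leaving these cases to be settled once the data are seen also leaves room for a choice that depends on the result.

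**Working it through.** The plan gives no power, alpha or effect size for PSADT, so there is no design figure to reproduce. The check applies the plan's own formula to its own visit schedule.

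**Inputs from the documents.** PSA weekly for two weeks, then at 1, 3, 6, 9, 12, 18 and 24 months (Table 7), which makes nine values by month 24. Trial 1 mean PSADT was 17 months before and 31 months after therapy (Table 2).

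**Assumptions, not in the documents.** Residual SD of ln(PSA) 0.05, 0.10 or 0.20; the PSA courses listed below; a prior doubling time of 17 months, borrowed from the Trial 1 mean.

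**1. Ordering.** PSADT = ln(2)/slope, with ln(2) = 0.693 and the slope per month:

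| Slope | PSADT (months) | Order by slope (1 = best) | Order by PSADT (1 = best) |
|---|---|---|---|
| +0.0408 | 17 | 4 | 3 |
| +0.0224 | 31 | 3 | 2 |
| +0.001 | 693 | 2 | 1 |
| −0.001 | −693 | 1 | 4 |

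The man whose PSA is not rising moves from best to worst. Ranking PSADT keeps that error, because ranks preserve the order of the values they are given.

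**2. A negative slope can follow a nadir.** Take invented values of 5.0 (nadir), 5.4, 5.3, 5.2 and 5.1 ng/mL at months 6, 9, 12, 18 and 24. Mean time is 13.8 months. The sum of squares of time is 208.8 and the cross-product with ln(PSA) is −0.1076. The slope is −0.1076/208.8 = −0.000515 per month, so PSADT is about −1,345 months for a PSA that has barely moved.

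**3. How often.** With truly flat PSA and independent noise, each of the nine values is equally likely to be the lowest, so the last is the nadir with probability 1/9 = 11%, whatever the SD. The other entries come from simulation, 20,000 runs per case, fitting least squares from the lowest value onward:

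| True course after injection | SD | No slope | Slope ≤ 0 | No usable PSADT |
|---|---|---|---|---|
| Flat | 0.05 to 0.20 | 11% | 11% | about 22% |
| Falling at half the prior rate (halving every 34 months) | 0.05 | 96% | 0% | 96% |
| Same | 0.10 | 78% | under 1% | 79% |
| Same | 0.20 | 52% | 6% | 58% |
| Halves by month 3 or 6, then doubles every 17 or 31 months | 0.05 to 0.20 | 0 to 2% | 0 to 1% | 0 to 2% |

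**4. Values that survive.** For flat PSA, where the true doubling time is infinite, the doubling time at the median slope among men with a fitted slope is about 120 months at SD 0.10 and 62 months at SD 0.20. Those figures reflect the noise, not the tumour.

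**The case against.** **Trial 1 did not show the problem.** Of 16 men, 14 had a post-treatment PSADT. The two losses were a death and early ADT, not response (Table 2 footnote). PSA falls lasted under 120 days (Section 1.2.2.1.2). This stands: if falls are as brief here, few men are affected, as the last row of the table shows. It does not supply the missing rule, and this vector adds IL-12 in the hope of greater activity.

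**Ranks handle extreme values.** They do for large positive ones. They do not for negative or missing ones.

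**The plan does not say that responders are dropped.** Correct. That is what the formula yields when nothing else is specified, and the cited method report, which was not available here, may contain a rule.

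**Fitting from the nadir is a legitimate choice.** It is: it targets the regrowth rate rather than the net trend. If PSA halves by month 6 and then doubles every 17 months, the nadir fit gives a median of about 16.4 months at SD 0.10, while one line through all post-treatment values gives about 312. With the nadir at month 12, the all-value slope is negative. A single line is therefore no better as the main analysis.

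**Stronger readings.** A reader might infer that the mandatory last pre-treatment PSA is inflated by the biopsy and so manufactures a benefit. The documents do not say that biopsy raises PSA, or by how much. A reader might also call PSADT the main activity signal, or the result uninterpretable. It is one of five secondary objectives, and PSA against baseline (Section 8.1.2.1) and freedom from PSA failure (Section 6.6.1) still capture sustained responders. Requiring three pre-treatment values is a declared minimum, not an error.

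**Conclusion.** The concern holds as a gap in the PSADT definition. Followed literally, Section 8.1.2.2 gives no value to a man still at his nadir and can give the worst-ranked value to a man whose PSA is level. That these cases arise follows from the formula alone. How often they arise depends on the assumed noise and PSA course: about 22% of men with flat PSA, 58% to 96% with slowly falling PSA, and at most about 2% with an early fall and regrowth. The share of men in each group is unknown, so no overall bias can be stated.

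A smaller asymmetry is also in the text. Post-treatment values stop at ADT, but pre-treatment values taken on and off ADT or Proscar can enter one slope. Its size cannot be judged from the documents, so it warrants a sensitivity analysis and no more. Dose escalation, toxicity and the MTD are untouched.

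**What to change.** Amend Section 8.1.2.2 before the PSA data are analysed:

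1. Compare the ln(PSA) slope before and after treatment, not its reciprocal, with a paired rank test read descriptively.
2. Give a man whose nadir is his latest PSA the most favourable rank, provided he has reached a stated minimum follow-up. Count men who die or start salvage therapy before that point as non-estimable, not as favourable.
3. Convert slopes to PSADT for display only, and list a slope of zero or below as *not doubling*.
4. Report the number non-estimable, with reasons.
5. Add two sensitivity analyses: one using all post-treatment PSAs instead of those from the nadir, and one leaving out pre-treatment PSAs taken on ADT or Proscar.

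Keep PSADT as now defined alongside, for comparison with Trial 1. The cost is a few lines of text and a little programming, with no new visits or samples. Drug dates are needed for the second sensitivity analysis, and some men may fall below three pre-treatment values in it; their number should be given.

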1.2.2.2.2 Results

Men in arm 1 exhibited a greater incidence of flu-like symptoms, transaminitis, neutropenia and

thrombocytopenia relative to men in arm 2. These events were expected and attributable to the oncolytic adenovirus (flu-like symptoms, transaminitis) and prodrug therapy (neutropenia, thrombocytopenia). The vast majority (98%) of AEs were grade 1/2 and transient. Less than 10% of men in each arm exhibited acute (\leq 90 days) \geq grade 2 GI toxicity. While acute \geq grade 2 GU events were more prevalent (arm 1- 43%, arm 2- 31%), no significant difference in acute GI or GU toxicity was noted between the two arms. There was no significant difference in QOL between the two treatment arms.

Prostate biopsy outcome \geq 2 years after radiotherapy is highly prognostic for long-term outcome (53-55). Hence, short-term efficacy was assessed by a 12 core prostate biopsy 2 years after completion of IMRT. Two-year biopsies were obtained on 37 (84%) men. There was a 42% ($P = 0.13$) and 34% ($P = 0.14$) relative reduction in biopsy positivity on arm 1 based on actual biopsies and intent-to-treat (ITT), respectively (**Table 4**). This type 1 error is within the accepted range for randomized phase 2 trials (56). There was a 60% ($P = 0.07$) and 48% ($P = 0.08$) relative reduction in biopsy positivity on arm 1 in men with < 50% positive biopsy cores at baseline based on actual biopsies and ITT, respectively. Owing to the adenovirus injection algorithm that skewed the adenovirus dose distribution to the positive sextants, men in arm 1 with < 50% positive cores received 2.5 times the adenovirus dose/positive core than men with \geq 50% positive cores.

To date, 1 subject in arm 1 (4.8%) and 2 subjects in arm 2 (8.7%) have exhibited biochemical failure. No subject has developed hormone-refractory or metastatic disease and none have died from prostate cancer.

Table 4. 2-Year Prostate Biopsy Results

		Subjects with Positive Biopsy ¹		P value
		Arm 1	Arm 2	
All subjects	Biopsied	6/18 (33%)	11/19 (58%)	0.13
	ITT ²	9/21 (43%)	15/23 (65%)	0.14
Stratification Group³				
1	Biopsied	0/1 (0%)	1/1 (100%)	> 0.99
	ITT	0/1 (0%)	1/1 (100%)	> 0.99
2	Biopsied	3/13 (23%)	8/14 (57%)	0.07
	ITT	5/15 (33%)	11/17 (65%)	0.08
3	Biopsied	3/4 (75%)	2/4 (50%)	0.47
	ITT	4/5 (80%)	3/5 (60%)	0.49
% Positive biopsy cores				
< 50%	Biopsied	3/13 (23%)	8/14 (57%)	0.07
	ITT	5/15 (33%)	11/17 (65%)	0.08
≥ 50%	Biopsied	3/5 (60%)	3/5 (60%)	> 0.99
	ITT	4/6 (67%)	4/6 (67%)	> 0.99

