¹Number of subjects with a positive 2-year biopsy over the total number of subjects with percentage in parentheses.

²Intent-to-treat (ITT) includes all subjects whether or not a 2-year biopsy was obtained. Those subjects that were not biopsied were given a positive score.

³Group 1- Gleason score 5/6 and PSA < 10 ng/mL and ≥ 50% positive biopsy cores. Group 2- (Gleason score 5/6 and PSA 10 - 20 ng/mL) or (Gleason score 7 and PSA 0 - 20 ng/mL) and < 50% positive biopsy cores. Group 3- (Gleason score 5/6 and PSA 10 - 20 ng/mL) or (Gleason score 7 and PSA 0 - 20 ng/mL) and ≥ 50% positive biopsy cores.

1.2.2.2.3 Summary of Results in Newly Diagnosed Setting In Combination With Contemporary Dose IMRT

There was no significant difference in GI/GU events and QOL between the two arms. There was a 42% relative reduction in 2-year biopsy positivity on the gene therapy arm (arm 1). There was a 60% relative reduction in 2-year biopsy positivity on the gene therapy arm in men who had < 50% positive biopsy cores at baseline. The results indicate that combining OAMCGT with contemporary dose IMRT does not exacerbate the most common side effects of prostate radiotherapy and results in a clinically meaningful reduction in positive biopsies at 2 years in men with intermediate-risk prostate cancer.

1.2.2.3 Newly Diagnosed Prostate Cancer In Combination With Conformal Radiotherapy and Non-Invasive Imaging (Trial 4)

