3.0 SUBJECT SELECTION

3.1 Number of Subjects

Fifteen to 30 men with locally recurrent prostate cancer after definitive radiotherapy.

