8.2 Sample Size Calculation/Power Justification for the Primary Endpoint

This is a MTD determination study. Therefore, the power calculation is not relevant. A 3 to 6 subject per dose cohort with a total of 15 to 30 subjects is standard for a phase 1 trial (72).

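### Hypothesis 3 on quality of life is worded as the null and judged only by significance tests in 15 to 30 men, with no margin or confidence interval

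*Combined protocol and SAP*

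**What the plan says.** Section 8.1.2.3 gives Hypothesis 3 as "Oncolytic adenovirus-mediated cytotoxic and IL-12 gene therapy has no significant effect on quality of life". Hypotheses 1 and 2 in the same section each assert an effect, on PSA and on PSA doubling time. Only Hypothesis 3 asserts the absence of one.

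QOL is measured with EPIC and EQ-5D at baseline and at 6, 12 and 24 months. Each domain is to be analysed by ANCOVA with the baseline score, time and a treatment variable. A treatment-by-time interaction is tested first at 0.10. If it is found, treatment is tested at each time point, with no level stated. If not, the plan goes on to "testing the overall treatment effect or time effect at critical value of 0.05 if otherwise". Transformation or a nonparametric method is allowed if data are not normal.

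On size, section 3.1 plans "Fifteen to 30 men with locally recurrent prostate cancer after definitive radiotherapy", and section 8.2 explains that "A 3 to 6 subject per dose cohort with a total of 15 to 30 subjects is standard for a phase 1 trial". On power, section 8.2 says: "Therefore, the power calculation is not relevant". Section 8.3 describes the analysis of the trial as descriptive.

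The documents give no equivalence or non-inferiority margin, smallest important change, standard deviation or confidence-interval criterion for any QOL score.

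**The concern.** A significance test can give evidence against a null hypothesis. Failing to reject it is not evidence that it is true. When the hypothesis to be supported is itself the null and the only tools are significance tests, a non-significant result is the outcome that agrees with it. Fewer men, noisier scores and missing forms all make that outcome more likely.

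Section 8.2 sets power aside, which is reasonable for finding a maximum tolerated dose. It is not a reasonable basis for a statement that draws support from a test failing to reject. What is at stake is one named secondary objective (section 2.2.5): the report could say that QOL was unaffected when the data are compatible with a material decline.

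**Working it through.** **1. The plan's own figure.** Table 5 has five cohorts of 3 to 6 men: 5 × 3 = 15 and 5 × 6 = 30. This reproduces the stated 15 to 30. The number follows from dose escalation and was not chosen for QOL.

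**2. Why the planned test cannot be given a power.** The ANCOVA needs a treatment variable, but every subject receives the study therapy and there is no control arm. The variable is undefined as written. A simpler test has to stand in for it, and what follows is an illustration.

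**3. Assumptions that are not in the documents.** Paired test of change from baseline at one visit; two-sided 0.05 (the plan gives no sidedness); complete data; normal change scores; a true fall of 0.5 SD of the change score.

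**4. Chance of missing the fall.** The test statistic follows a noncentral t with n − 1 degrees of freedom and noncentrality 0.5 × √n. Miss probability = 1 − power.

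| n | Critical t | Noncentrality | Power | Missed |
|---|---|---|---|---|
| 15 | 2.145 | 0.5 × 3.873 = 1.94 | 0.438 | 56.2% |
| 30 | 2.045 | 0.5 × 5.477 = 2.74 | 0.754 | 24.6% |

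A simulation of 200,000 trials per sample size gave 56.3% and 24.6%.

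**5. If the half SD refers to the raw score.** With correlation r between baseline and follow-up and equal variances, SD of change = raw SD × √(2(1 − r)). The standardised effect is 0.5 / √(2(1 − r)).

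| r | Effect in SD of change | Missed, n = 15 | Missed, n = 30 |
|---|---|---|---|
| 0.7 | 0.5 / 0.775 = 0.65 | 36% | 7% |
| 0.5 | 0.5 / 1.000 = 0.50 | 56% | 25% |
| 0.3 | 0.5 / 1.183 = 0.42 | 67% | 39% |

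**6. Other choices (n = 15 / n = 30).** One-sided 0.05: 42% / 15%. Raw-score half SD, mean of the three post-treatment visits at r = 0.5: 40% / 10%. With 12 or 24 men completing the form and 0.5 SD of change: 65% / 35%. If the treatment variable meant dose cohort, comparing two cohorts of 3 or of 6 would miss a half-SD difference in about 92% or 88% of trials.

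**7. Precision of an estimate.** The half-width of the 95% confidence interval for mean change, in SD of change, is t(0.975, n − 1) / √n: 2.145 / 3.873 = 0.55 at n = 15 and 2.045 / 5.477 = 0.37 at n = 30.

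**The case against.** The best reply is section 8.3. If the whole analysis is descriptive, no test result decides anything. No dose decision, stopping rule or formal claim depends on QOL, and tolerability is judged on dose-limiting toxicity. This stands as a limit on severity. It does not remove the point, because section 8.1.2.3 still sets out a hypothesis and tests with critical values, and nothing says which section governs.

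Second, the 0.05 test is not the only rule: the interaction step at 0.10 comes first. That is correct, but it too is a significance test without a margin.

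Third, the percentages describe a test that the plan does not specify, and they treat one domain as the whole hypothesis. This also stands. If a 0.5-SD fall affected three domains and the tests were independent, all three would be missed in about 0.562³ = 18% of trials at n = 15 and 0.246³ = 1.5% at n = 30. Correlation between domains moves these back towards 56% and 25%. The plan does not say how domain results combine into one conclusion.

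A reader might also infer from the background on the randomised phase 2 trial (Trial 5) that the sponsor will treat non-significance as proof. There, acute grade 2 or higher GU events were 43% against 31%, section 1.2.2.2.2 reports that "no significant difference in acute GI or GU toxicity was noted between the two arms", and section 1.2.2.2.3 concludes that the combination "does not exacerbate the most common side effects of prostate radiotherapy". That passage concerns toxicity chiefly, in another trial with another vector and radiotherapy. It sets no rule for QOL here, and the point does not rest on it.

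**Conclusion.** The point holds as a fault of wording and inference in a secondary endpoint. Hypothesis 3 is the null, the only stated tools are significance tests, and a non-significant result in 15 to 30 men cannot support it. This conclusion needs no numerical assumption. The conflict with section 8.3 is part of the same fault.

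The size is illustrative. The 56% and 25% rest on the paired single-visit test and on an effect of 0.5 SD of change. The range for half a raw-score SD is wide, and the documents give nothing with which to narrow it.

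Two stronger readings are tempting and not supported. One is that this trial will miss a half-SD fall at a fixed rate of 25% to 56%, or at least at that rate when data are complete. Averaging visits or a high baseline correlation gives lower figures, and the planned model has no defined treatment contrast to which any rate could be attached. The other is that non-significance is a formal success criterion that will carry a tolerability claim into later development. The documents attach no such decision to QOL.

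**What to change.** Restate Hypothesis 3 in section 8.1.2.3 as an estimation aim: mean change from baseline for each QOL domain at 6, 12 and 24 months, with 95% confidence intervals. This agrees with section 8.3 and does not need the undefined treatment variable. Add a sentence that a non-significant test will not be reported as absence of effect. If any test is kept, say that it is supportive and define what it compares.

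A margin is not needed for this repair. If the sponsor wishes to state that there was no material decline, it should do so only when the lower 95% limit lies above a margin fixed in advance. The choice of margin is the sponsor's. The direction reverses for the EQ-5D items, where a higher score is worse.

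The cost is an edit to the hypothesis and the replacement of the ANCOVA sequence. No extra subjects, visits or data are needed. The drawback is a less favourable statement, often inconclusive, especially at n = 15. With an illustrative margin of 0.5 SD of change and a true change of zero, the lower limit would clear the margin in 44% of trials at n = 15 and 75% at n = 30. An 80% chance would need 34 men, above the planned maximum. A single-arm interval also cannot separate the effect of treatment from disease course or later salvage therapy, and the report should say so.
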